1.0 OBJECTIVE

- 1.1 To assess the efficacy in terms of reduction in Ki-67(as a surrogate endpoint to breast cancer risk reduction) in patients treated with anastrozole.
- 1.2 To measure the histopathological response and correlate the degree of histopathological response with the degree of Ki-67 response.
- 1.3 To compare pretreatment vascular density with post treatment vascular density using MRI
- 1.4 To compare pretreatment markers of angiogenesis with post treatment marker of angiogenesis.
- 1.5 To correlate MR imaging response to markers of angiogenesis response.
- 1.6 To correlate ER, Ki-67, angiogenesis markers and MRI response to histopathological changes

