ER expression will be demonstrated with the DAKO 1D5 mouse monoclonal and PgR with the Novocastra antibody NCL-PgR clone 1A6 For all other analytes, 10 high-powered fields (chosen randomly) will be assessed. ER and PgR will be reported as percentage of positively stained cells.

2. **Dynamic Contrast Enhanced MRI as a Secondary Marker to Quantify Chemoprevention by Anastrozole**

We have investigated the relationship between endoglin (CD105), a marker selectively associated with neo-vascular endothelium, and vascular volume density in early breast cancer. The patients had a preoperative contrast enhanced dynamic MRI and the tissue blocks obtained at surgery were immunohistochemically (IHC) stained for CD105. The dynamic contrast enhanced MRI images were then analyzed by using the compartmental modeling technique as described by us previously to quantify vascular density VB (Su, 1995; Su, 1994; Su, 1998; Su, 1999). The result shown in the next figure summarizes our finding that shows a strong correlation between vascular density (VB) and CD105 score suggesting that the MRI technique to be used in the current investigation provides a measure of tumor angiogenesis in breast cancer.

In another study, Gilles et al. performed preoperative contrast material-enhanced subtraction

dynamic MR imaging in thirty-six women with DCIS. Concomitant early contrast enhancement in the breast parenchyma with normal vessels was considered a positive finding. The size and shape of early enhancement were correlated with the size and density packing of ducts involved by DCIS. Their results indicate that early contrast enhancement was demonstrated in 34 patients with DCIS but not in two patients with comedo-type DCIS. Tumor angiogenesis was demonstrated in the stroma. The size and morphology of contrast-enhanced lesions significantly correlated with the size ($P = .0085$) and density packing of ducts involved by DCIS ($P = .012$). They conclude that enhancement on dynamic MR images of DCIS may be due to the presence of tumor angiogenesis in the stroma (Gilles, 1995).

MRI study that is described below will be repeated twice, once before the therapy at baseline and once after the therapy.

2.a Imaging Technique:

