10.0 CRITERIA FOR EVALUATION AND ENDPOINT DEFINITIONS

10.1 Absolute percent Ki-67 change pre anastrozole and post anastrozole as well as percentage of patients achieving less Ki-67 less than 10%

10.2 Histopathological response.

A complete response (CR) indicating the disappearance of the primary tumour; a partial response (PR) indicating a reduction of $\geq 50\%$; stable disease (SD) indicating a reduction of $< 50\%$ or increase in size of $< 25\%$; progressive disease (PD) indicating an increase in size of $\geq 25\%$.

The pathological CR will be evaluated by tumour excision and axillary node resection (in case of invasive breast cancer only). Two grading classifications will be utilised to evaluate the tumour response after chemotherapy. In the Chevallier classification, the absence of invasive tumour cells, or persistence of *in situ* disease, and negative axillary lymph nodes define a pathological CR. In the Sataloff classification, we have similar criteria for a pathological CR, but also observe the persistence of small clusters of widely dispersed cells in these cases.

We will correlate patients with degree of drop of Ki-67 with degree of pathological response

10.3 MRI is obtained at the base line and 4 weeks after anastrozole.

MRI characteristics pre and post anastrozole

10.4 IHC determination of markers of angiogenesis and ER, PR and pre anastrozole and post anastrozole expressed as IHC scores and percentage.

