11.0 STATISTICAL CONSIDERATIONS

Statistical Power: In this non-randomized trial, the primary surrogate marker will be Ki-67. Individuals who exhibit at least 40% reduction in Ki-67 from baseline will be categorized as responders. For p = probability of response, the null hypothesis is specified as p_0 , and the alternative as p_1 . Our null hypothesis is that after 4 weeks of therapy, no more than 5% of the subjects will exhibit at least 40% decrease in Ki-67 levels. Table 1 gives the number of subjects necessary to detect differences of 25% to 45% from the null proportion of 5%, using the binomial test with a significance level of 0.05. Thus, for 90% power, 24 evaluable subjects are necessary to detect a difference of 25% from the null. Because of the necessity of working with patients with a small tumor size all patients accrued may not be evaluable. We anticipate a non-evaluability rate of 50% as quoted by experienced investigators. Hence, we will accrue 42 patients on this trial.

In this non-randomized trial, the primary surrogate marker will be Ki-67 level.

Table 1. Number of subjects, $p_0 = 0.05$

p_1	80% Power	90% Power
0.30	18	24
0.35	12	18
0.40	10	12
0.45	9	10
0.50	5	9

All of the quantitative results generated by IHC (percentage of eg. Ki67) will be given as their arithmetic mean levels. The comparison of changes in proliferation markers and receptor levels between responders and nonresponders will be performed using the Mann-Whitney U test.

The Primary outcome is response to treatment. For each participant, the post-treatment level of Ki-67 will be compared to the pre-treatment level of ki-67. If at least a 40%

decrease from the pretreatment level achieved, the participant will be classified as a responder. The proportion responding and the 95% confidence interval for this proportion will be calculated. The 2-sided binomial test with $\alpha = 0.05$ will be performed to test $p_0 = 0.05$ vs. $p_0 \neq 0.05$.

The secondary aims of the study are to evaluate change from baseline in the MRI parameters, vascular volume (V_b) and K_2 . The distribution in changes from baseline in tumor estrogen, V_b , and K_2 will be examined using probability plots. The Kolmogorov-Smirnov goodness-of-fit test for normality will be performed. If indicated, normalizing transformations will be applied. Ninety-five percent confidence intervals for mean change from baseline and mean percent change from baseline will be computed.

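### Comparing ER/PgR change across the 40% Ki-67 split is valid but ignores the size of the Ki-67 change; if the correlation is 0.4-0.6 and 30-50% respond, this costs about 14-25 points of power

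*Combined protocol and SAP*

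**What the plan says.** Section 11.0 plans one analysis that relates receptor change to response: "The comparison of changes in proliferation markers and receptor levels between responders and nonresponders will be performed using the Mann-Whitney U test". The same section defines the groups: "Individuals who exhibit at least 40% reduction in Ki-67 from baseline will be categorized as responders". It repeats that rule for the primary outcome, gives no other definition, and names no correlation or regression method.

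Both quantities are recorded on fuller scales. Section 10.1 lists "Absolute percent Ki-67 change pre anastrozole and post anastrozole" as an endpoint. Section 2.0 (Other Tissue Biomarkers) says "ER and PgR will be reported as percentage of positively stained cells", and Section 10.4 calls for ER and PR before and after anastrozole.

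The correlations planned elsewhere do not cover this pair:
- Objective 1.6 reads "To correlate ER, Ki-67, angiogenesis markers and MRI response to histopathological changes", so it ties ER to histopathology.
- Section 10.2 ties the degree of Ki-67 fall to pathological response.
- The Specific Aims in Section 2.0 tie angiogenesis markers and MRI to Ki-67.

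None relates receptor change to the size of the Ki-67 change.

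**The concern.** Cutting Ki-67 change at 40% treats a 39% fall like a rise, and a 41% fall like a 95% fall. The cut is needed for the primary responder proportion. It is not needed to ask whether receptor change moves with Ki-67 change, since both are available as percentages.

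The plan expects only about two dozen evaluable patients and a 50% non-evaluable rate, so paired specimens are scarce. What is at stake is the precision of one secondary comparison, not the trial's main conclusion.

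**Working it through.** **Step 1. The plan's own figures.** Section 11.0 states no power, significance level or expected correlation for the Mann-Whitney comparison, so there is no figure of that kind to reproduce. The sample size comes from the primary test: "for 90% power, 24 evaluable subjects are necessary to detect a difference of 25% from the null". Under an exact binomial test at two-sided 0.05 (0.025 in the upper tail), nine of the ten Table 1 cells reproduce. The exception is p1 = 0.30 at 90% power: the smallest n is 21 (power 91.4%), and n = 24 gives 88.9%. That mismatch is a separate matter. Here it only sets the range of N: 24 as stated, and 42 × (1 − 0.50) = 21 from the accrual target.

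**Step 2. Inputs.**
- N = 24 and 21 (Section 11.0).
- Responder share 0.30 to 0.50 (the p1 values in Table 1).
- Two-sided 0.05. This is stated for the primary test and assumed here.
- Correlation rho between Ki-67 change and receptor change: assumed, main range 0.4 to 0.6, with 0.3, 0.7 and 0.8 as sensitivity values.
- Bivariate normal changes: assumed.

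**Step 3. Method.** 20,000 simulated trials per setting. Ki-67 change is split at the point that gives the stated responder share. The exact Mann-Whitney test on receptor change between the groups is compared with Spearman's r_s on the uncut data, using t = r_s √[(n − 2)/(1 − r_s²)] on n − 2 degrees of freedom. The standard error of each power is at most √(0.25/20,000) = 0.35 points.

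**Step 4. Results at N = 24.**

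| Share | rho | Spearman | Mann-Whitney | Loss (points) |
|---|---|---|---|---|
| 0.30 | 0.3 | 26.3% | 16.7% | 9.6 |
| 0.30 | 0.4 | 45.2% | 28.4% | 16.8 |
| 0.30 | 0.5 | 66.7% | 43.1% | 23.6 |
| 0.30 | 0.6 | 84.9% | 60.7% | 24.3 |
| 0.30 | 0.7 | 96.1% | 78.4% | 17.7 |
| 0.30 | 0.8 | 99.7% | 91.9% | 7.8 |
| 0.50 | 0.3 | 27.1% | 18.5% | 8.6 |
| 0.50 | 0.4 | 45.1% | 31.4% | 13.7 |
| 0.50 | 0.5 | 66.2% | 47.3% | 18.9 |
| 0.50 | 0.6 | 85.1% | 66.9% | 18.1 |
| 0.50 | 0.7 | 96.1% | 84.3% | 11.7 |
| 0.50 | 0.8 | 99.7% | 96.0% | 3.7 |

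For rho 0.4 to 0.6 the loss is 13.7 to 24.3 points, or about 14 to 25 allowing for simulation error. At N = 21 it is 13.1 to 26.6. With rho = 0 at N = 24, rejection is 4.8% and 4.7% for Mann-Whitney and 5.1% and 5.3% for Spearman (shares 0.30 and 0.50), so both tests hold their level.

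**Step 5. Sensitivity (normal-approximation Mann-Whitney).**
- Ties: with roughly half of receptor changes set to zero, the loss at N = 24 and rho 0.4 to 0.6 is 12.5 to 24.7 points.
- Step relation: if receptor change depends only on being a responder (shift 0.8 to 1.3 standard deviations), Mann-Whitney gains 9.9 to 23.7 points at N = 24.
- Lopsided split: at a share of 0.15 or 0.85, outside the Table 1 alternatives, the loss reaches about 42 points (N = 24, rho 0.6).

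**The case against.** **It is a preference, not an error.** Mann-Whitney holds its level, and the groups come from the trial's prespecified primary outcome. No objective or specific aim concerns receptor change against Ki-67 response, and the plan attaches no hypothesis or power to this comparison. All of this stands, and it is why the point is minor.

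***Responders* may mean something else.** The sentence also compares proliferation markers between the groups, which is circular for Ki-67 if Ki-67 defines them. Reading the word as histopathological responders (Section 10.2) avoids that, and the point would then not apply. Section 11.0 defines only the Ki-67 responder, so the literal reading is used here, but the ambiguity is real.

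**The size is conditional.** A reader might infer a flat loss of 14 to 25 points. The documents give no correlation, and Step 5 shows that the sign reverses under a pure step at 40%. Nothing in the documents suggests such a step.

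**A real link would be missed more often than found.** A reader might infer this for moderate correlations. It is true of Mann-Whitney at 0.4 and 0.5, but not at 0.6 (61% and 67% power at N = 24). At 0.4 Spearman also misses more often than it finds (45%). N is small for either method.

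**The test might be unable to reach significance at all.** With one responder in 24 the smallest two-sided exact p is 2/24 = 0.083. At p1 = 0.30, however, the chance of at most one responder is 0.7^24 + 24 × 0.3 × 0.7^23, about 0.2%. It is about 66% only under the plan's null rate of 5%.

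**Conclusion.** The point holds as a minor efficiency gain in a secondary comparison. On Section 11.0's only definition of responder, the planned test is valid but discards the measured size of the Ki-67 change, and no other planned analysis recovers it for ER and PgR.

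The cost of about 14 to 25 points at 24 evaluable patients rests on three assumptions: a correlation of 0.4 to 0.6, a responder share of 30% to 50%, and a graded rather than step relation. The documents support only the second, through Table 1. They do not support calling the test wrong, or saying that the trial's conclusions are at risk.

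**What to change.** In Section 11.0, state that the relation between receptor change and Ki-67 change will be analysed mainly by Spearman's rank correlation with a 95% confidence interval. Correlate percent change in Ki-67 with change in ER, and separately with change in PgR, over all patients with paired values. Keep the responder/nonresponder comparison of receptor change as description. Say in the same place which *responders* are meant.

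Percent change is undefined when baseline Ki-67 is zero, so either use absolute change or exclude those patients, and state which. Leave the primary responder proportion and its binomial test as they are.

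The cost is a few sentences, with no new patients, assays or visits. There are two small downsides. A correlation is less direct to read than two group summaries. And because Ki-67 and the receptors come from the same core and surgical specimens, shared sampling differences could contribute to the correlation, which should be said when it is reported.

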The plasma levels of free estradiol are very low in postmenopausal women. However, concentrations of estrogens within breast tissue have been reported to be higher than in plasma

and similar to plasma concentrations in premenopausal women. One mechanism by which this may occur is for breast cells to synthesize estrogens themselves and produce high concentrations locally. An investigation by Brodie et al. suggests that estrogen produced locally is important in enhancing proliferation of the tumor (Brodie, 1998). In this study, they used immunocytochemical method using a monoclonal antibody to determine the expression of aromatase (Brodie, 1998). The method was applied to sections of tumors embedded in paraffin blocks as routinely prepared for pathology. Both immunocytochemistry and in situ hybridization identified aromatase enzyme and mRNA expression in the epithelial cells of the terminal ductal lobula units (TDLU) and surrounding stromal cells of the normal human breast, and in the tumor epithelial cells and stromal cells of breast cancers. Thus, tumor aromatase may be a significant source of estrogen which stimulates tumor growth (Brueggemeier, 2001). The finding that significantly higher levels aromatase expression levels were found in DCIS than in infiltrating ductal carcinoma indicates that it may be possible to treat DCIS patients with aromatase inhibitors (Zhang 2002).

We propose to undertake a Phase II a chemoprevention clinical trial in women with ductal carcinoma in situ (DCIS) and early breast cancer using aromatase inhibitors. In order to assess efficacy of the chemoprevention of such drugs, we propose to employ reduction in tumor Ki-67 as the primary surrogate marker with dynamic contrast enhanced MRI as a secondary marker. Other immunohistochemical markers such as p53, thrombospondin-1, CD31, CD105, and VEGF will also be used as exploratory markers for changes in angiogenesis in response to therapy. Histopathological reversal of preinvasive and early invasive breast cancer will also be evaluated.

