Angiogenesis plays a fundamental role in tumor growth and metastasis. Investigations by Teruyama et al. and Mastuyugin et al. have established a relationship between VEGF expression and p450 aromatase activity (Teruyama, 2001; Mastuyugin, 2002). We have previously shown that dynamic contrast enhanced MRI in conjunction with compartmental modeling may be used to assess the angiogenic status of tumors while enabling the study of both breasts (Su, 2002). Additionally, image based measurement techniques do not suffer from the errors due to tissue heterogeneity and use of limited spatial sampling imposed in methods such as histology. Furthermore, MRI based parameters that describe breast physiology have been found to correlate well with immunohistochemically measured angiogenesis markers (Su, 1995; Su, 1994; Su, 1996). *Thus, dynamic contrast enhanced MRI will be used as a secondary surrogate marker in the proposed study.*

Methodology to test the hypothesis: Core biopsies will be obtained from patients whose mammographic findings are suspicious for DCIS. Patient will undergo MRI study prior the biopsy. At the time of biopsy, a portion of the tissue retrieved will be sent in formalin for histopathological examination for Ki-67, ER, PR and angiogenesis markers evaluation.

1 mg of anastrozole administered orally daily for 4 weeks after the diagnosis of DCIS/invasive breast cancer. The reason for using a 4-week regimen is that this is the average time between diagnostic biopsy and definitive lumpectomy or mastectomy.

Patients will undergo MRI at baseline before therapy and then again after anastrozole treatment that will be followed immediately by definitive surgical procedure, i.e. lumpectomy or mastectomy. Lumpectomy/mastectomy specimen will be again evaluated for the level of tumor

Ki-67 decline and the level of angiogenesis markers. The specimen will be subjected to the routine histopathological, and ER and PR evaluation. Histopathological changes pre and post anastrozole will be evaluated in an exploratory analysis.

Detailed Methodology

1. **Quantification of Ki-67 as a Primary Marker to Monitor Response to Chemoprevention by Aromatase Inhibitor Anastrozole**

Measurement of Ki-67 Levels.

[figure not shown]
Measurement of **Ki67** will be performed with the MIB1 mouse monoclonal antibody. To ensure acceptable precision, quantitation of Ki67 will involve the counting of 1000 cells.

Other Tissue Biomarkers.

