Angiogenesis controls with intermediate vessel counts will be run in parallel with each series of slides to insure appropriate CD31 staining. An invasive breast carcinoma specimen with high microvascular staining will be used for the positive control, and the nonstaining areas in the same tumor tissue will be used for the negative control. Light microscopy will be used to identify three regions within or immediately adjacent to the tumor that contained the greatest microvessel density ("hotspots"). Microvessel counts were then performed using a x200 field within the designated hotspot. Of the three areas where the highest number of discreet microvessels are stained, the area of greatest counts will be chosen for scoring. Any immunoreactive endothelial cell that is separate from adjacent microvessels is considered a "countable" vessel.

Image Analysis.

On the basis of the intracellular and extracellular localizations of TSP-1, tumor expression levels of TSP-1 were measured by image analysis as described previously to integrate overall tissue expression levels. Briefly, we used a CAS 2000 two-color system (Becton Dickinson, San Jose, CA) that used a light microscope attached to an interactive microcomputer capable of high-speed digital image processing for cell measurements. Image channels were matched to two-component immunohistochemical staining to enhance the image of one stain in each channel. One channel was used to identify all components in the tissue counterstained with methyl green (*i.e.*, all nuclear components), and the other channel was used to calculate the density of brown stain (diaminobenzidine) per tissue area to identify the proportion of cells stained with antibodies to TSP-1. Image analysis-based units of staining are reported as absorbance (*A*). A negative control

accompanying each specimen was used to set the antibody threshold such that nonspecific background staining was eliminated from the study measurement. A minimum of 10 fields with varying intensities were examined for all radical prostatectomy, transurethral prostatectomy, or biopsy specimens.

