Immunohistochemistry of p53, TSP-1, CD31, CD105, and VEGF will be analyzed as markers of angiogenesis. We expect to observe a greater anti-angiogenic effect in the tumor with the higher angiogenic activity (i.e. with a higher CD31 and CD106 vessel density or a higher VEGF before treatment). According to pre-treatment CD31, CD105, or VEGF, the tumors will be categorized into 3 groups with high, medium, and low angiogenic activities. Normalizing transformations for each variable will be considered. We will evaluate these parameters using analysis of variance to test for reduction from baseline, followed by the sequentially rejective Bonferroni procedure for multiple comparisons to maintain an overall significance level of 0.05. Changes in p53 and TSP-1 will be evaluated similarly.

Data Safety and Monitoring Committee (DSMB)

This study will be monitored throughout accrual and follow-up periods by the UCI Data Safety and Monitoring Board (DSMB). There is a single DSMB to monitor all UCI therapeutic trials. This committee is responsible for reviewing interim analyses prepared by the study statistician and for recommending whether the study needs to be modified or terminated based on these analyses. This committee also determines when the study results will be submitted for publication or otherwise released to the public. It will review any major modifications to the study proposed by the Study Committee. The Study Committee is responsible for monitoring the data from the study for toxicity, feasibility, and accrual. The study committee also initiates minor changes in the study such as clarification of eligibility criteria.

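### Grouping tumours by a marker's own baseline and then testing change from that baseline by ANOVA lets regression to the mean produce the result the plan expects

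*Combined protocol and SAP*

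**What the plan says.** Section 11.0 states a directional expectation for the angiogenesis markers: "We expect to observe a greater anti-angiogenic effect in the tumor with the higher angiogenic activity". It then defines the groups: "According to pre-treatment CD31, CD105, or VEGF, the tumors will be categorized into 3 groups with high, medium, and low angiogenic activities". The markers are to be evaluated "using analysis of variance to test for reduction from baseline". A multiplicity step comes after the ANOVA; the plan describes it as "followed by the sequentially rejective Bonferroni procedure for multiple comparisons to maintain an overall significance level of 0.05". The other two markers follow the same route: "Changes in p53 and TSP-1 will be evaluated similarly". Normalizing transformations will be considered.

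The section does not name the ANOVA factor or give cut-points for the three groups. It does not say whether each marker is grouped on its own baseline or all markers share one classification.

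The same section describes a non-randomized trial, and Section 7.0 gives a single regimen. Under the methodology in Section 2.0, the baseline reading comes from part of a core biopsy and the later one from the lumpectomy or mastectomy specimen. No replicate baseline is described.

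Section 2.0 is not uniform on the status of these markers. In one place they "will also be used as exploratory markers for changes in angiogenesis in response to therapy"; Specific Aim 4 lists them as a secondary surrogate for risk reduction.

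**The concern.** A baseline reading is the tumour's true level plus error. Sorting on that reading puts tumours with positive errors disproportionately in the high group and those with negative errors in the low group. The second reading carries a fresh error, so the high group falls on average and the low group rises, with no drug effect. That is the gradient the plan says it expects.

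The error is not hypothetical. In arguing for MRI, Section 2.0 itself refers to "errors due to tissue heterogeneity and use of limited spatial sampling imposed in methods such as histology", and the two readings come from different tissue samples. For the microvessel count, "the area of greatest counts will be chosen for scoring", so that score rests on a single selected field.

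Nothing in Section 11.0 guards against this. The transformations address distribution shape and the Bonferroni step addresses multiplicity; neither removes a bias in the group means. At stake is a formal claim, at an overall 0.05, that anastrozole acts more strongly in highly angiogenic tumours. Section 2.0 intends these results to inform the choice of surrogate endpoint for later trials.

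**Working it through.** **Sample size.** The plan gives no size or power for this analysis, so there is no figure of its own to reproduce here. Section 11.0 accrues 42 and anticipates 50% non-evaluable: 42 × 0.5 = 21. The 24 evaluable subjects named for the Ki-67 test serve as a second case.

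**Assumptions, not in the documents.** Reliability r = 0.5, 0.7 or 0.9; normal scores; equal thirds (7 per group at n = 21); no drug effect; the marker is grouped on its own baseline; group is the ANOVA factor.

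**Model.** Pre = T + e₁ and post = T + e₂, with T ~ N(0, r) and independent errors N(0, 1 − r). Each reading has SD 1 and the pre–post correlation is r. Then E(post − pre | pre) = −(1 − r) × pre.

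**Size of the spurious fall.** In large samples the top third of a standard normal has mean 1.09, so the expected high-group change is:
- r = 0.5: −0.5 × 1.09 = −0.55 SD
- r = 0.7: −0.3 × 1.09 = −0.33 SD
- r = 0.9: −0.1 × 1.09 = −0.11 SD

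With 7 of 21 per group, simulation gives slightly smaller falls of 0.53, 0.31 and 0.10 SD, mirrored by a rise in the low group.

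**False rejection.** 400,000 simulated null trials per setting, n = 21:

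| Analysis | r = 0.5 | r = 0.7 | r = 0.9 |
|---|---|---|---|
| ANOVA between groups, 0.05 | 42.0% | 24.7% | 10.5% |
| ANOVA at 0.05/3 (nominal 1.7%) | 24.6% | 12.3% | 4.2% |
| High-group fall, Holm over 3 groups (0.8% without the bias) | 12.7% | 7.2% | 3.0% |
| Low-group rise, Holm over 3 groups | 12.6% | 7.1% | 3.0% |
| Both of these together | 2.3% | 0.9% | 0.2% |
| Overall change, ANOVA within-group error, 0.05 | 7.6% | 6.4% | 5.4% |
| Ungrouped paired test, 0.05 | 5.0% | 5.0% | 5.0% |

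The overall test with within-group error runs slightly high because grouping on baseline removes part of the variance of the change from its error term.

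**Sensitivity.**
- n = 24: ANOVA at 0.05 rejects in 48.3% / 28.6% / 11.6%; the Holm high-group fall occurs in 15.5% / 8.6% / 3.4%.
- Unequal groups at n = 21 (low/medium/high 5/11/5, 9/7/5 or 5/7/9; 40,000 trials): ANOVA 41–42% / 24–25% / 10–11%.
- Reliability 0.95, n = 21: ANOVA 7.6% at 0.05.
- Marker grouped by a different marker (true values correlated 0.5; 40,000 trials), ANOVA at 0.05: 4.9% / 5.0% / 4.9% with uncorrelated baseline errors, 6.3% / 5.7% / 5.2% at error correlation 0.25, and 12.1% / 9.2% / 6.3% at 0.5.

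**The case against.** The strongest objection is that the plan does not state the test being criticised. A between-group ANOVA on change asks whether groups differ, whereas the sentence speaks of testing for a reduction, which fits a pre/post comparison and Specific Aim 4. The multiplicity step could run across the five markers rather than the three groups. On that reading the error rate is at most 7.6% in the table above. The ambiguity is real. Still, the groups have no other stated use and the stated expectation compares groups, so group as the factor is the natural reading.

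Second, coverage may be narrow. The word *or* in the grouping sentence allows one classification for all tumours, in which case only one marker would be grouped on itself. p53 and TSP-1 are not listed as grouping variables. This stands: the bias then reaches the other markers only through correlated baseline errors.

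Third, stricter versions of the plan shrink the figures. At 0.05/5 for five markers, ANOVA rejects in 18.7% / 8.7% / 2.8%, against a nominal 1%. If the ANOVA must first reach 0.05, the Holm high-group fall drops to 10.7% / 5.3% / 1.8%. A significant pooled fall together with a significant ANOVA occurs in only 0.9% / 0.5% / 0.2% of null trials, so the overall change shown beside the groups is a useful check. These versions reduce the problem without removing it.

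Fourth, reliability is assumed throughout. Section 2.0 has some analytes scored over ten random fields, which lowers within-specimen error but not the error from sampling a core. Nor does the hotspot rule alone create regression to the mean. At high reliability the harm is slight.

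Finally, Section 2.0 calls the markers exploratory and Section 11.0 gives the MRI parameters as the secondary aims. That limits the consequences, but the plan still tests the markers formally.

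**Conclusion.** The concern holds for any marker grouped on its own baseline with group as the ANOVA factor. The planned comparison is then biased toward the stated expectation, and the design offers no means of separating the artefact from a drug effect. At n = 21 the false rejection rate at 0.05 runs from 42.0% at reliability 0.5 to 10.5% at 0.9. The harm is therefore substantial to slight, depending on a quantity the documents do not supply.

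Regression to the mean leaves the pooled mean change and an ungrouped paired test unaffected. The Ki-67 primary test and the MRI intervals are untouched. The point should be corrected but does not threaten the main result. Confidence is medium, because the ANOVA factor and the grouping rule have to be inferred.

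**What to change.** Replace the grouped test in Section 11.0 with wording such as: *For each marker, change from baseline will be tested with one ungrouped paired test and 95% CI over all evaluable tumours, after any normalizing transformation, with the sequentially rejective Bonferroni procedure across markers at an overall 0.05. Results by baseline high/medium/low group are descriptive only; regression to the mean produces such a gradient without a drug effect.*

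The cost is wording only, on the same data. The subgroup expectation is no longer formally tested, and a paired test does not remove any systematic difference between core-biopsy and surgical specimens.

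Power of the paired test for a fall of 0.5 baseline SD at n = 21, from the noncentral t with SD of change √(2(1 − r)) = 1.00 / 0.77 / 0.45 for r = 0.5 / 0.7 / 0.9:
- at 0.05: 59% / 80% / >99%
- at 0.05/3 (first Holm step, three markers): 40% / 64% / 99%
- at 0.05/5 (first Holm step, five markers): 32% / 55% / 98%

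If the team wants to keep a formal test of the gradient, grouping on the mean of the pre and post readings held the ANOVA at 4.8% to 5.2% under no effect. This requires equal pre and post variances, which is uncertain when the two specimens differ in type.
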